4.2 Intervention

The study will consist of three phases: screening, treatment, and follow-up.

Screening Phase:

- Establishment of initial eligibility and signing of the informed consent.
- Confirmation that tumor tissue from a metastatic or loco-regionally recurrent lesion is available for biomarker analysis; if none is available and biopsy not an option, with the permission of the principal investigator, tumor tissue from the primary site at initial diagnosis is acceptable.
- HPV status will be determined via p16 IHC staining or HPV ISH or PCR for all oropharynx primaries. The p16 staining will be interpreted as positive if $>70\%$ strong and diffuse nuclear and cytoplasmic staining is specific to tumor cells. Status will be reported dichotomously as positive or negative. EBER staining will be reported as well for patients with nasopharynx cancer. For non-oropharynx and non-nasopharynx primaries, these tests are not required. Tests previously

performed on primary tumor specimens from oropharynx or nasopharynx lesions at time of diagnosis are sufficient to meet this criterion.

- Baseline tumor assessments will be performed within 28 days of randomization.
- Eligibility assessment per timeframe outlined.
- The screening phase will conclude with either randomization of the subject or with confirmation that the subject is a screen failure.

Treatment Phase:

- Nivolumab should begin within 14 days (+/-4 days) of randomization. The first day of Nivolumab is designated as study Day 1.
- Radiation will be delivered over 3 treatments (9 Gy per treatment) to a single lesion. The first fraction must be administered by study day 14. The remaining 2 radiation treatments will be delivered over 10 business days at a frequency no greater than every other day.
- All of the laboratories and vital signs will be collected prior to study drug dosing at the time points specified.
- Adverse events will be documented at the time points specified.
- Biomarker and immunogenicity samples will be obtained according to the outlined schedules.
- EORTC QLQ-C-30: will be completed by Day 1 of treatment, and then, starting at week 8 (+/- 2 weeks), every 8 weeks (+/-2 weeks) for the first 48 weeks and every 12 weeks (+/- 2 weeks) until either week 96 or disease progression (whichever occurs first).
- Nivolumab is administered as an IV infusion every 14 days (+/- 2 days) until disease progression (or until discontinuation of Nivolumab in subjects receiving beyond progression), unacceptable toxicity, or withdrawal of consent.
- Response is evaluated using RECIST 1.1 criteria.

The first tumor assessment of non-irradiated lesions will occur at week 8 (+/- 2 weeks) after treatment initiation and then every 8 weeks (+/-2 weeks) for the first 48 weeks and then every 12 weeks (+/-2 weeks) until documented progression or week 96 whichever occurs first. CT or MRI images of chest, abdomen, pelvis, head, neck, and all known sites of disease should be obtained. The same imaging modality that was used as baseline should be used at all subsequent evaluations.

- After week 96 of treatment, patients will be contacted every 3 months for survival. This can be done by phone if the patient is unable to come into clinic for routine follow-up.
- Treatment phase will conclude at the time of study drug discontinuation.
- Imaging can continue per institutional preference past 96 weeks, however, RECIST reads are not required.

Follow-Up Phase

- Begins at the conclusion of Nivolumab therapy.

- Subjects will have one follow-up visit for safety within approximately 100 days from the last dose of Nivolumab.
- Subjects who discontinue treatment for reasons other than tumor progression will continue to have tumor assessments per prior schedule (e.g. every 8 weeks for the first 48 weeks and then every 12 weeks until week 96).
- Follow-up (phone or visit) will continue to occur every 3 months for survival information.

5.0 THERAPEUTIC/DIAGNOSTIC AGENTS

5.1 Nivolumab (BMS-936558)

Nivolumab is a fully human monoclonal immunoglobulin G4 antibody that binds to the programmed death-1 (PD-1) cell surface membrane receptor, a negative regulatory molecule expressed by activated T and B Lymphocytes.

Nivolumab has a concentration of 10mg/mL and is provided in a 10mL vial. Nivolumab infusion concentration must be at or above the minimum allowable concentration of 0.35 mg/mL.

Nivolumab will be provided by BMS (Bristol-Myers Squibb) and shipped directly to the site where it is to be administered.

Nivolumab (OPDIVO) is approved for the treatment of unresectable or metastatic melanoma in multiple countries including Japan, the US, and EU. It is also approved for the treatment of metastatic squamous cell NSCLC in the US.

5.1.1 Storage Conditions and Handling

Nivolumab should be stored at between 2-8 degrees Celsius (36-46 degrees Fahrenheit), and protected from light, freezing, and shaken. If any temperature excursions are encountered during storage, they should be reported to BMS. As with all injectable drugs, care should be taken when handling and preparing Nivolumab. Whenever possible, Nivolumab should be prepared in a laminar flow hood or safety cabinet using standard precautions for the safe handling of intravenous agents applying aseptic technique. Partially used vials should be disposed at the time following procedures for the disposal of anticancer drugs.

5.1.2 Use Time/Stability

Once transferred to IV bags, the solution may be stored for up to 20 hrs in a refrigerator at 2-8 degrees Celsius and used within 4 hours at room temperature and under room light inclusive of administration time. The maximum 4-hour period under room temperature and room light conditions for undiluted and diluted solutions of Nivolumab injection in the IV bag should be inclusive of the product administration period. Please refer to the current Investigator Brochure for further details (Section 3).

5.2 Image-Guided, High Dose Stereotactic Body Radiotherapy

Image-guided, stereotactic body radiotherapy allows for the delivery of high-dose-per-fraction radiotherapy with exquisite precision while excluding to a large degree normal tissue from being exposed to high-dose regions of irradiation. Stereotactic radiotherapy is defined as the directing of therapy using beams of radiation along any trajectory in 3D space toward a target of known 3D coordinates. The coordinate system is defined by reliable fiducial markers. For the purposes of this study, the tumor itself will serve as the fiducial. Low-dose CT scans will be obtained at the time of treatment delivery, and intensity modulated radiotherapy planning (IMRT) will be utilized.

IMRT is a sophisticated radiation planning and delivery technique that uses a computer controlled multi-leaf collimator to shape the intensity of each radiation treatment beam to optimally deliver the dose to the tumor and protect normal tissue. The radiotherapy delivery systems that will be used in this trial are standard and FDA approved. The dose fractionation scheme (9 Gy x 3) has been used routinely at MSKCC and other tertiary care centers.

6.1 CRITERIA FOR SUBJECT ELIGIBILITY

In order for a patient to be enrolled on trial, the following criteria need to be met:

6.2 Subject Inclusion Criteria

1) Signed Written Informed Consent

- Subjects must have signed and dated an IRB/IEC approved written informed consent form in accordance with regulatory and institutional guidelines.
- Subjects must be willing and able to comply with scheduled visits, treatment schedule, laboratory testing, and other study obligations.

2) Target Population

- Males and females ≥ 18 years of age.
- Eastern Cooperative Oncology Group (ECOG) performance status ≤ 2 .
- Histologically confirmed metastatic HNSCC, including nasopharynx WHO Type I-III histologies; patients can have simultaneous loco-regional disease. Central biopsy review at MSKCC is not required.
- Subjects must have at least two lesions:
 - At least one lesion must be safely amenable to irradiation and likely to meet criteria delineated in Section 9.2.1 in the judgment of the treating radiation oncologist. This can be a lesion that was previously irradiated as long as prior radiation was at least 6 months prior to projected first fraction of SBRT and as long as reirradiation dose constraints as outlined in appendix are being met.
 - A separate, not-to-be-irradiated lesion measurable by CT or MRI per RECIST 1.1 criteria.
- A formalin fixed, paraffin-embedded (FFPE) tumor tissue block or a minimum of 3 unstained slides of tumor sample obtained via excisional, incisional, or core needle biopsy from a metastatic or loco-regionally recurrent lesion. A new baseline biopsy does not need to be obtained for study purposes. If 3 unstained are unavailable from

a metastatic or loco-regionally recurrent lesion, with permission of the PI, FFPE tumor tissue from the primary disease site at the time of original diagnosis is acceptable.

- For oropharynx or nasopharynx primary lesions, documentation of viral status is required (e.g. high risk HPV sub-type PCR, p16 IHC, HPV ISH, EBER, etc). Tests done on primary tumor specimens from date of initial diagnosis at outside institutions are sufficient to meet this criterion.
- Prior palliative or curative radiotherapy must be completed at least 14 days prior to randomization.
- Immunosuppressive doses of systemic medication, such as steroids or absorbed topical steroids (doses >10mg/day prednisone or equivalent) must be discontinued at least 14 days prior to first Nivolumab administration.
- Screening laboratory values must meet the following criteria (using CTCAE v4.0) and should be obtained within 28 days prior to randomization:
 - WBC \geq 2 K/microliter
 - Neutrophils \geq 1.5 K/microliter
 - Platelets \geq 100 K/microliter
 - Hemoglobin \geq 9.0 g/deciliter
 - Serum Creatinine \leq 1.5 x ULN or creatinine clearance $>$ 40ml/min using the Cockcroft-Gault formula.
 - *Female* CrCl = $\frac{(140 - \text{age in years}) \times \text{weight in kg} \times 0.85}{72 \times \text{serum creatinine in mg/dL}}$
 - *Male* CrCl = $\frac{(140 - \text{age in years}) \times \text{weight in kg} \times 1.00}{72 \times \text{serum creatinine in mg/dL}}$
 - AST/ALT \leq 3 x ULN (for subjects with liver metastases AST/ALT may be \leq 5 x ULN).
 - Total bilirubin $<$ 1.5 x ULN (except subjects with Gilbert Syndrome who can have total bilirubin $<$ 3.0 mg/deciliter)
 - Calcium levels must be normalized and maintained within normal limits for study entry and while on treatment.
 - Subjects with an initial magnesium $<$ 0.5 mmol/liter (1.2 mg/deciliter) may receive corrective magnesium supplementation but should continue to receive either prophylactic weekly infusion of magnesium and/or oral magnesium supplementation.
 - Subjects must have a resting baseline O2 saturation by pulse oximetry of \geq 92% at rest.

3) Reproductive Status

- Women of childbearing potential must have a negative serum or urine pregnancy test (minimum sensitivity 25 IU/L or equivalent units of HCG) within 28 days prior to randomization.
- Women must not be breastfeeding

- Women of childbearing potential must agree to follow instructions for method(s) of contraception from time of enrollment for the duration of treatment with Nivolumab plus 5 half-lives plus 30 days for a total of 23 weeks post treatment completion.
- Men who are sexually active with WOCBP must use any contraceptive method with a failure rate of less than 1% per year. Men receiving Nivolumab and who are sexually active with WOCBP will be instructed to adhere to contraception for a period of 31 weeks after the last dose of investigational product.
- Women who are not of childbearing potential (i.e., who are postmenopausal or surgically sterile as well as azoospermic men do not require contraception.
- Azoospermic males and women of childbearing potential who are continuously not heterosexually active are exempt from contraceptive requirements. However, they still must have a pregnancy test.

4) Insurance Approval

- Insurance approval for SBRT should be obtained prior to randomization

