3.4.2 Rationale for Timing of Radiotherapy and Nivolumab

Although not completely analogous, Witek, et al reported on timing of radiotherapy relative to the administration of an adenoviral-mediated vaccine against the colorectal cancer antigen GUCY2C in a murine subcutaneous tumor model using mouse CT26 colon cancer cells [30]. They found that T cell responses were enhanced and tumor eradication maximized when RT was administered prior to the vaccine.

Deng, et al, in their study of anti-PD-L1 antibody in combination with RT delivered the therapies on the same day or with anti-PD-L1 given 1 day prior to RT administration. Golden, et al, in their report of an abscopal effect seen with the combination of Ipilimumab and radiation NSCLC-adenocarcinoma, delivered the RT one day prior to the Ipilimumab.

Recognizing the paucity of data, but based on the aforementioned reports, this study will involve the administration of the first dose of Nivolumab one day **before** the first fraction of radiation.

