6.2 Subject Exclusion Criteria

Target Disease Exceptions

- Active brain metastases (untreated brain metastases or growth on imaging as defined below) or leptomeningeal disease are not allowed. Subjects with brain metastases are eligible if these have been treated and there is no MRI (or CT if MRI contraindicated) evidence of progression for at least 8 weeks after treatment for these metastases is complete and within 28 days prior to first study treatment.
- Histologically confirmed non-squamous histologies are not allowed; an exception is made for WHO Type I-III nasopharynx histologies.

Medical History and Concurrent Diseases:

- Any medical disorder that, in the opinion of the investigator, might increase the risk associated with study participation or interferes with the interpretation of study results.
- Prior active malignancy within the previous 3 years except for locally curable cancers such as basal or squamous skin cancer, superficial bladder, low risk prostate cancer, breast, or cervix cancer. If other prior malignancy was active within prior 3 years, enrollment requires approval of a principal investigator.
- Patients should be excluded if they have an active, known or suspected autoimmune disease. Subjects are permitted to enroll if they have vitiligo, type I diabetes mellitus, residual hypothyroidism due to autoimmune condition only requiring hormone replacement, psoriasis not requiring systemic treatment, or conditions not expected to recur in the absence of an external trigger
- Subjects with a condition requiring systemic treatment with either corticosteroids (> 10 mg daily prednisone equivalents) or other immunosuppressive medications within 14 days of study drug administration should be excluded. Inhaled or topical steroids and adrenal replacement doses >10mg daily prednisone equivalents are permitted in the absence of active autoimmune disease.

- As there is potential for hepatic toxicity with Nivolumab, drugs with a predisposition to hepatotoxicity should be used with caution in patients treated with Nivolumab-containing regimen.
- Prior treatment with an anti-PD-1, anti-PD-L1, or anti-PD-L2 antibody.
 - NB-patients who have received prior anti-CTLA-4 antibody therapy are eligible assuming such therapy was discontinued within 28 days of enrollment.
- Treatment with any chemotherapy, radiation therapy, biologics for cancer, or investigational therapy within 14 days of randomization.

Physical and Laboratory Test Findings

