8.1.2 Safety Assessments

- Assessment of Signs and Symptoms within 28 days prior to randomization
- Physical Examination within 28 days prior to randomization
- Physical Measurements: weight within 28 days prior to randomization
- Vital Signs and Oxygen saturation: blood pressure, heart rate, temperature, O2 saturation via pulse oximetry within 28 days prior to randomization
- Performance status within 28 days prior to randomization
- Prior medication collection: data on all prior systemic therapy received to treat HNSCC within 28 days prior to randomization
- Concomitant Medication Collection: obtained within 28 days prior to randomization
- Laboratory Tests (obtained within 28 days prior to randomization)
 - Complete Blood Count
 - Comprehensive Metabolic Panel (AST, ALT, TBili, BUN, Creatinine, Ca, Mg, Na, K, Cl, Glucose, Amylase, Lipase)
 - TSH, Free T4, T3
 - Hepatitis B surface antigen, hepatitis C antibody
- Pregnancy Test within 28 days prior to randomization.

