9.1 TREATMENT/INTERVENTION PLAN

Nivolumab should begin within 14 days (+/-4 days) of randomization. The first day of Nivolumab is designated as study Day 1.

Arm 1: On Day 1, patients will receive a one hour infusion of Nivolumab 3mg/kg and then every 14 days (+/-2 days) until treatment progression per RECIST 1.1 criteria, unacceptable toxicity, or withdrawal of consent.

Arm 2: After randomization, patients will complete CT simulation. On Day 1 they will receive their first dose of Nivolumab (3mg/mg); they will receive their first radiation treatment (9 Gy) by study day 14. The additional 2 fractions of radiation (9 Gy per fraction) will be delivered within 10 business days, no more frequently than every other day. Nivolumab 3mg/kg will be administered

every 14 days (+/-2 days) until treatment progression per RECIST 1.1 criteria, unacceptable toxicity, or withdrawal of consent.

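### The only pregnancy test the protocol text requires is at screening; with no repeat after randomisation, a negative result can be 42 days old at first nivolumab (46 with the tolerance)

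*Combined protocol and SAP*

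**What the plan says.** **The test.** Section 6.2 (Subject Inclusion Criteria, Reproductive Status) says that any potentially fertile woman "must have a negative serum or urine pregnancy test (minimum sensitivity 25 IU/L or equivalent units of HCG) within 28 days prior to randomization". Section 8.1.2 repeats the requirement: "Pregnancy Test within 28 days prior to randomization". The study calendar following Section 10.2.2 has one mark in the pregnancy-test row, in the screening column. The first-dose and pre-dose laboratory list in Section 10.1.1 contains no hCG, and the SBRT simulation, planning and delivery sections (9.2.2 and 9.2.3) require no test.

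**The exposures.** Section 4.2 (Intervention) states: "Nivolumab should begin within 14 days (+/-4 days) of randomization". That first dose defines study Day 1. For Arm 2, Section 9.1 says "they will receive their first radiation treatment (9 Gy) by study day 14". The timing rationale in Section 3.4.2 describes "the administration of the first dose of Nivolumab one day before the first fraction of radiation", but the treatment sections set only the day-14 limit.

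**The safeguards.** Women of childbearing potential "must agree to follow instructions for method(s) of contraception from time of enrollment for the duration of treatment with Nivolumab" and for 23 weeks after treatment ends. Those who are continuously not heterosexually active are exempt from contraception but must still be tested. Pregnancy is always handled as an SAE (Section 17.3) and in most cases ends study treatment permanently (Section 17.2.3).

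**The concern.** The test is tied to randomisation, but what it guards against is exposure to nivolumab and, in Arm 2, to 27 Gy of SBRT. The interval between the two is not covered by any test in the text supplied. A woman can meet every written rule and start treatment with an early pregnancy that was undetectable at screening or that followed a contraceptive failure. The SAE and discontinuation rules act only once a pregnancy has been discovered. Fetal radiation dose depends on the target and is likely small for distant lesions, but Section 9.2.1 (Target Selection) does allow abdominal-pelvic targets.

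The protocol already treats screening chemistry as too old for dosing: blood counts and chemistry taken within 28 days before randomisation are repeated within 48 hours of the first dose. The pregnancy test is not. What is at stake is patient safety at low frequency. The comparison of response rates is not involved.

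**Working it through.** The plan states no figure for the age of the test at first exposure, so there is none to reproduce. The check adds up the permitted windows.

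**Inputs**
- Test to randomisation: up to 28 days (Sections 6.2 and 8.1.2).
- Randomisation to first nivolumab: 14 days, tolerance 4 days (Sections 4.2 and 9.1).
- First SBRT fraction: by study day 14, which is 13 days after Day 1 (Section 9.1).
- Laboratory sample: within 48 hours before first nivolumab (calendar footnote A).

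**Maximum age of the negative result as written**

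| First exposure | Nominal start | With +4 days |
|---|---|---|
| Nivolumab, Day 1 | 28 + 14 = 42 days | 28 + 18 = 46 days |
| SBRT one day later (rationale only) | 42 + 1 = 43 days | 46 + 1 = 47 days |
| SBRT on study day 14 | 42 + 13 = 55 days | 46 + 13 = 59 days |

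The start window is worded as advice, so these are maxima within the stated windows and not absolute caps.

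**Expected contraceptive failures between test and first nivolumab.** The number of women of childbearing potential is not given. I assume 1 to 6 of the 60 patients. The only failure rate in the text is for men's methods, "any contraceptive method with a failure rate of less than 1% per year"; I assume 1% to 10% per year for women. Expected failures = women × annual rate × days/365.
- Low: 1 × 0.01 × 42/365 = 0.001.
- Six women at 1%: 6 × 0.01 × 46/365 = 0.008.
- High: 6 × 0.10 × 46/365 = 0.076, about 0.08.

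These count failures over the whole interval, not pregnancies that a repeat test would find; a conception shortly before Day 1 would still be missed. Conceptions too early for the screening test come on top and cannot be estimated from the documents.

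**Maximum age after the change.** At most 48 hours (2 days) at first nivolumab and 72 hours (3 days) at first SBRT. If SBRT follows one day after nivolumab, a sample drawn 48 hours before dosing is 48 + 24 = 72 hours old, so it serves for both. A sample drawn 48 hours before dosing covers SBRT to study day 2; one drawn on Day 1 covers it to study day 4. At a day-14 fraction the pre-nivolumab sample is 13 to 15 days old and a second test is needed.

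**Number of assays.** Fewest: 1 woman needing one test = 1. Most: 6 women, all in Arm 2, two tests each = 12. Randomisation is stratified by viral status only, so six women in one arm is possible.

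**The case against.** The strongest reply is that this is a consistent convention with very little to gain. Almost all screening assessments are timed to randomisation. Contraception applies from enrolment, and Section 15.3 places registration immediately after consent, so most of the interval is protected. The upper estimate of 0.08 needs six women, a 10% annual failure rate and the longest permitted gap for every one of them. At 1% it is 0.008. A Day 1 test has its own blind spot for very recent conceptions, and the later two-weekly doses would still rely on contraception. All of this stands, and it is why the point is modest.

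It does not remove the gap. Contraception cannot reveal a pregnancy that screening missed. Some requirements are already timed to exposure: evidence of stable brain metastases must fall "within 28 days prior to first study treatment", and the steroid washout is counted back from nivolumab. Shortening the screening window would be simpler and would avoid post-randomisation withdrawals, but even a test on the day of randomisation would be 14 to 18 days old at first nivolumab and 27 to 31 days old at a day-14 SBRT fraction (14 + 13 and 18 + 13).

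A reader might infer more than the text supports:
- *That no pregnancy test precedes exposure.* The mandatory screening test does. What is missing is a repeat.
- *That the sites do not retest.* Consent pages and contraception instructions are not in the text supplied, appendices are filed separately, and the protocol defers to the Investigator Brochure. The finding is limited to the text at hand.
- *That first nivolumab is the last chance to avoid all exposure.* Section 9.1 describes Arm 2 CT simulation before Day 1, so some low-dose imaging exposure can come earlier.
- *That one sample will normally serve both exposures.* The one-day interval appears only in the rationale. The operative rule is day 14, so a second Arm 2 test may often be needed.

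**Conclusion.** The point holds as a low-frequency safety gap with a cheap remedy. In the protocol text supplied, the only required pregnancy test may be 42 days old at first nivolumab, 46 with the tolerance, and 55 to 59 days old at a day-14 first SBRT fraction. These ages follow directly from the stated windows.

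The expected yield of a repeat test is very small. The 0.001 to 0.08 range rests on assumed numbers of women and assumed failure rates, and it counts failures arising rather than exposures averted. Nothing here affects the type I error, power or treatment comparison. The case rests on a potentially serious consequence set against a negligible cost. It covers first exposure only; retesting during treatment is a separate decision.

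**What to change.** Keep the screening test as the eligibility criterion. Add the following to Section 10.1.1 and the study calendar, with a one-line cross-reference in Sections 9.1 and 9.2.3:

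> Women of childbearing potential: hCG on the sample drawn within 48 hours before the first nivolumab dose; a negative result is required before dosing. Arm 2: a negative urine or serum hCG within 72 hours before the first SBRT fraction is also required; the pre-nivolumab sample counts if it falls within that window.

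This wording does not cover the Arm 2 CT simulation. The sponsor could time a test to it as well.

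**Cost.** A few lines of text and about 1 to 12 assays if 1 to 6 women of childbearing potential enrol. The pre-nivolumab assay uses blood already being drawn.

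**Downside.** A positive or unclear result may delay the first dose. A rare confirmed pregnancy would leave a randomised, untreated patient. She stays in the all-randomised set for PFS and OS, but her place in the ORR analysis is unclear. The primary objective in Section 14.0 divides by all patients randomised to the arm, whereas the population list in the same section restricts the ORR set to those with at least 6 months of follow-up after treatment initiation. One such patient is 1/30 = 3.3% of an arm. Section 14.0 also replaces patients lost to follow-up before 6 months without saying whether this case qualifies. One sentence should settle both her denominator and her replacement.
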